8.3.2.2 HbA1c and FPG

Blood samples for FPG and HbA1c measurements will be collected and analysed (in local laboratories) as part of standard clinical practice at each site. The date and results of the most recent test will be recorded at every visit.

The secondary effectiveness endpoint HbA1c (see Section [7.3.2.1](#)) (change from baseline to during treatment) is the most widely accepted measure of overall, long-term blood glucose control in patients with diabetes.

8.3.2.3 Body weight

Body weight (kg) measurements will be collected, if available. Patients should ideally be weighed in their underwear or without shoes, on an appropriately calibrated weighing scale, as per standard clinical practice. Where possible the same weighing scales should be used throughout the study.

8.3.2.4 Serious adverse drug reactions (SADRs), medical events of special interest (MESI) and pregnancies

SADRs, severe hypoglycaemic events (regardless of seriousness or causality), MESI (medication errors), and pregnancies will be recorded throughout the study, from the signature of the informed consent form until the end of the study as defined by the protocol for that patient (see Section [10](#)).

All SADRs will be coded using the latest version of Medical Dictionary for Regulatory Activities.

8.3.2.5 Documentation of insulin dose and time of injection

Patients will be provided with a study diary and requested to prospectively document daily Tresiba[®] doses for 4 weeks prior to each physician visit.

At each visit the Tresiba[®] dosage details (time, amount, and date of each dose) should be transcribed from the patient dose record into the eCRF.

At each visit, the patient will be asked what their total daily dose of bolus insulin was on the day prior to the visit, if applicable and this will be entered into the eCRF.

8.3.2.6 Self-measured blood glucose (SMBG)

Patients will be provided with a study diary and requested to document the number of SMBG test strips used over the 4 weeks prior to each physician visit. The SMBG measurements should not be performed unless according to clinical practice at the site.

8.3.2.7 Patient reported outcomes (PROs)

All PRO questionnaires should be completed by the patients at every visit (see [Table 8–1](#)); preferably before any other study-related activities. All PROs will be available in the local languages.

Health-related quality of life (HR-QoL)

The SF-36 health status survey assesses general health status. HR-QoL will be measured via the SF-36 v2 instrument. The SF-36 has 36 questions grouped into eight domains termed: physical functioning; bodily pain; role-physical; general health; vitality; social functioning; role-emotional; and mental health, which again can be combined to give two summary component scores.

The patient should complete SF-36 (version 2) at every visit.

Diabetes Treatment Satisfaction Questionnaire (DTSQ)

The status DTSQ (DTSQs) provides a measure of how satisfied patients are with their treatment and how they perceive hyper- and hypoglycaemia in the real world clinical setting. It consists of 8 questions, which are to be answered on a Likert scale from 0 to 6. The change version (DTSQc) has the same 8 items as the status version, but is reworded to measure the change in satisfaction rather than absolute satisfaction. Each item is scored on a scale of -3 to +3.

Patient should complete the DTSQs at visits 1, 2, 3, 4, 5, and 6 and the DTSQc at visit 6.

8.3.3 Other assessments

8.3.3.1 Health economics (HE)

HE endpoints will be collected using the patient diary (collected at visits 2, 3, 4, 5, and 6).

Patient diary:

At visits 1, 2, 3, 4, and 5, patients will be provided with a study diary and requested to document the resources used due to hypoglycaemia, over a 4-week period prior to each physician visit. The treating physician, or an appropriately trained member of staff, should enter the HE data into the eCRF which will contain specific fields based on the diary.

Patients will be encouraged to record information such as, if they have:

- had any outpatient visits due to hypoglycaemia
- had any physician or diabetic nursing visits due to hypoglycaemia
- had any treatment at home by a paramedic, due to hypoglycaemia
- had any emergency room visits, due to hypoglycaemia
- needed ambulance transportation, due to hypoglycaemia
- been hospitalised due to hypoglycaemia and duration of any hospital stays
- had any days absent from work due to hypoglycaemia
- used SMBG test strips and how many.

8.3.3.2 Reason for switching or not switching to Tresiba[®]

When recording data at visit 2, the treating physician will also be asked to identify, and enter into the eCRF, the most important factor determining his/her decision to switch the patient to Tresiba[®] (for all patients who sign the informed consent including those who switch during the 4-week baseline period) or not to switch the patient to Tresiba[®], as applicable.

8.3.3.3 Flexibility of dose time and FlexTouch[®] pen device

The effects of dose-time flexibility on compliance and effectiveness will be measured by collecting data from patient diaries. At each visit, the treating physician, or an appropriately trained member of staff, should document the dose-time flexibility responses in the eCRF which will contain specific fields based on the diary.

Patients will be provided with a study diary and requested to prospectively document information on missed doses and dose-time flexibility 4 weeks prior to each physician visit.

Patients will be asked to record/indicate information such as:

- If they miss a dose
- Why they missed a dose
- What did they do when they missed a dose
- How often they needed to take their Tresiba[®] at a different time/used the possibility of dose-time flexibility

In addition, at visits 2-6, the patient will be asked if their insulin treatment required them to change any social, leisure, and working time activities.

At the end of the study, patients will be asked which they found easier to use a) the FlexTouch[®] pen or b) previous injection method.

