- Change from baseline (visit 2) in health-related quality of life (HR-QoL) questionnaire scores (PROs: Short form-36 [SF-36] and Diabetes Treatment Satisfaction Questionnaire [DTSQ]) after 12 months of treatment
- Change from baseline in HE-endpoints (eg, number of physician visits, emergency room visits, etc, listed in Section [7.3.2.4](#)) after 12 months of treatment
- Patient preference compared to previous treatment
- FlexTouch[®] pen; preference of this device compared to previous injection method before Tresiba[®] use at the end of the study
- Change from baseline in dose-time flexibility endpoints after 12 months of treatment

The following secondary endpoints will be used in external registration of the study at clinicaltrials.gov and the ENCePP register:

- Change from baseline in HbA1c and FPG after 12 months
- Change from the baseline period in the number of severe hypoglycaemic episodes after 12 months
- Change from baseline in HR-QoL questionnaire scores (PROs: SF-36, and DTSQ) after 12 months of treatment

All data reported as counts will be converted to rates per PYE for analysis purposes.

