7.3.2.4 Health economic and dose-time flexibility endpoints

- Physicians primary reason for switching to treatment with Tresiba[®] (see Section [8.3.3.2](#))
- Physicians primary reason for not switching to treatment with Tresiba[®] (see Section [8.3.3.2](#))
- Physicians primary reason for switching to treatment with Tresiba[®] during the baseline period ie, early switchers (see Section [8.3.3.2](#))
- Change from baseline in the following HE-endpoints:
 - Number of outpatient visits due to hypoglycaemia
 - Number of physician or diabetic nursing visits due to hypoglycaemia
 - Number of treatments by a paramedic at home
 - Number of emergency room visits due to hypoglycaemia
 - Number of ambulance transportations due to hypoglycaemia
 - Number of hospitalisations due to hypoglycaemia, and duration of hospitalisation
 - Duration of absence from work due to hypoglycaemia
 - Used SMBG test strips and how many
- Patient preference compared to previous treatment
- FlexTouch[®] pen; preference of this device compared to previous injection method before Tresiba[®] use at the end of the study
- Change from baseline in dose-time flexibility endpoints:
 - Number of missed doses
 - Reason for missed dose
 - Action taken when dose missed
 - Changes in any social, leisure, and working activities due to insulin treatment
 - Number of times Tresiba[®] flexibility option used

All data reported as counts will be converted to rates per PYE for analysis purposes.

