³ Patient diaries will include sections for recording information such as details of hypoglycaemia, insulin dosage, dose-time flexibility, and health economics resource use.

⁴ Each SADR will be spontaneously reported and recorded on a separate AE and safety information form according to existing reporting procedures. MESI includes medication errors.

⁵ Four weeks prospective hypoglycaemia assessment leading up to visits at Months 0, 3, 6, 9, and 12, in addition to a 6 month severe hypoglycaemia recall at visit 1.

⁶ Patients will be encouraged to fill the PRO questionnaires, preferably before any other study related procedures.

⁷ Status version of DSTQ at visits 1, 2, 3, 4, 5 and 6, change version of DSTQ at visit 6.

⁸ Preference of FlexTouch[®] over previous injection method.

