8.4.6 End of Study (Visit 6, Month 12)

Treating physicians will perform and record details of the last visit as described in Section [8.4.5](#). Patients will continue to be treated as directed by their physician. Patients will be asked to return any diaries; after this visit no further data will be collected. Patients will be asked at the end of study visit which they found easier to use a) the FlexTouch[®] pen or b) previous injection method.

End of the study will have no impact on the treatment decision made by the physician.

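### The FlexTouch endpoint is defined as device preference, but the only device question asks which was easier to use, with two listed answers

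*Protocol*

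**What the plan says.** The endpoint is defined in two sections and labelled in a third place, always as preference:

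- Section 3.6.2, for the FlexTouch pen at the end of the study: "preference of this device compared to previous injection method before" Tresiba use.
- Section 7.3.2.4, in the health economic and dose-time flexibility list: "preference of this device compared to previous injection method before Tresiba" use.
- Table 8-1, footnote 8, attached to the visit 6 item: "Preference of FlexTouch" and then "over previous injection method".

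The question put to patients is specified in two places, both times as ease of use:

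- Section 8.3.3.3: "At the end of the study, patients will be asked which they found easier to use", followed by option a), the FlexTouch pen, and option b), the previous injection method.
- Section 8.4.6: "Patients will be asked at the end of study visit which they found easier to use", with the same two options.

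Section 8.3.3.4 has a separate preference question at visits 3 to 6. It compares Tresiba with the previous treatment. Section 3.9 says that categorical endpoints are shown as N and %.

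**The concern.** Ease of use is one part of preference, not the whole of it. A patient can find one pen easier to handle and still prefer the other method for a different reason. The protocol nowhere says that ease of use stands in for preference. If the plan is followed as written, a percentage will be reported as device preference although no patient was asked which device they prefer.

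The answer list is a second, smaller weakness. With only the two devices offered, the answers do not distinguish a patient with a clear view from one who sees no difference and ticks a box anyway.

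Both problems are fixed when the data are collected. An analysis plan could rename the result, but it could not recover a preference that was never recorded.

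**Working it through.** The check is mainly a comparison of text. The protocol gives no expected percentage, sample size or power for this endpoint, so there is no figure to reproduce.

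**Step 1: endpoint against question**

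| Place | Role | Construct |
|---|---|---|
| 3.6.2 | endpoint definition | device preference |
| 7.3.2.4 | endpoint definition | device preference |
| Table 8-1, footnote 8 | label of the visit 6 item | device preference |
| 8.3.3.3 | question asked | ease of use, two listed answers |
| 8.4.6 | question asked | ease of use, two listed answers |
| 8.3.3.4 | another question | treatment preference, not device |

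Three places name one construct and two collect another. The only other candidate, 8.3.3.4, concerns the treatment and cannot fill the gap. It does show that the protocol asks directly about preference when it wants to; it does not do so for the device.

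**Step 2: what two answers can show**

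This step is illustrative, and none of its inputs is in the protocol. Let *u* be the share who see no difference, *a* the FlexTouch share among those with a view, and *s* the share of the indifferent who tick FlexTouch.

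- With a neutral answer, FlexTouch share = (1 − *u*) × *a*.
- With two answers, all of them used, FlexTouch share = (1 − *u*) × *a* + *s* × *u*.

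Take *u* = 0.30 and *a* = 0.50:

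- With a neutral answer: 0.70 × 0.50 = 35%.
- Two answers, *s* = 0: 0.35 + 0 = 35%.
- Two answers, *s* = 0.5: 0.35 + 0.15 = 50%.
- Two answers, *s* = 1: 0.35 + 0.30 = 65%.

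Over a range of *u*, with *a* = 0.50:

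| Indifferent (*u*) | FlexTouch, neutral answer offered | FlexTouch, two answers (*s* from 0 to 1) |
|---|---|---|
| 10% | 45% | 45–55% |
| 20% | 40% | 40–60% |
| 30% | 35% | 35–65% |
| 40% | 30% | 30–70% |

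The width of each range equals *u*. The previous method's share runs over the same range in mirror image, because *a* = 0.50, so the table says nothing about which device gains.

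The table covers the answer list only. The gap between ease of use and preference has no figure in the protocol and is not quantified here.

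**The case against.** The strongest reply is that this is a terminology slip in a minor endpoint. Ease of use may be a reasonable proxy for device preference, and aligning the label with the question would end the contradiction. That stands as a limit on importance. The endpoint is not primary, is not among those for external registration (7.3.2.5), and is not named in the categorical list in 8.7.2.2. That it will appear as a percentage is inferred from the general rule in 3.9.

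A second reply is that 8.3.3.3 and 8.4.6 only summarise the question. The eCRF page is not shown and could carry a neutral answer, and 8.6.2 lets an item be marked as not done or not applicable. This stands in part. It would be too strong to say that every indifferent patient is forced to choose a device. But 'not done' or 'not applicable' is not the same as 'no difference', and the protocol lists no such answer. The mismatch of constructs remains either way.

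Three stronger readings are tempting, and the documents do not support them:

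- *Indifferent patients would favour the current pen.* There is no control group and the item comes at month 12, so this is conceivable, but nothing in the protocol shows a direction.
- *Some patients may have used the same or a similar device before.* The protocol mentions FlexTouch only as the Tresiba pen, excludes prior Tresiba users (8.2.3), and does not describe earlier devices.
- *The planned 15% withdrawals would all go unscored.* Section 8.4.2 already asks that last-visit procedures be recorded at premature withdrawal where possible. Some answers may still be missing, but counting all withdrawals as missing, or as not preferring the pen, follows no rule in the protocol.

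**Conclusion.** The point holds as a contradiction between the endpoint and its measurement. As written, the planned data can show which device patients found easier to use, but not which they prefer. That conclusion rests on the text alone and needs no numerical assumption.

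That the item does not separate indifferent patients rests on the two answers listed in the protocol, and would fall away if the eCRF page carries a neutral answer. Its size is unknown. The range of 35% to 65% depends on an assumed 30% indifferent and an even split among the rest; it is two-sided and is not evidence of inflation.

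The importance is low. The primary endpoint, the sample size and the safety conclusions are unaffected. What changes is the claim that can be made about the pen.

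**What to change.** Make the endpoint and the question agree, in one of two ways:

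1. **Measure preference.** In 8.3.3.3 and 8.4.6, ask which device the patient prefers, with three answers: FlexTouch, previous method, no preference. The wording in 3.6.2, 7.3.2.4 and footnote 8 can then stay.
2. **Measure ease of use.** Keep the question, rename the endpoint ease of use in 3.6.2, 7.3.2.4 and footnote 8, and add a no-difference answer in 8.3.3.3 and 8.4.6.

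In either case, report all three categories with their denominator and the number not answered. If the eCRF already has a neutral answer, the protocol should state it. If some patients have already answered the two-answer form, show the two forms separately.

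The cost is a small protocol and eCRF amendment, including ethics committee submission under 9.3. The sponsor may also see a less favourable percentage for its pen, because indifferent patients would be counted in their own category.

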8.3.3.4 Patient preference

At each physician visit after initiation of Tresiba[®] treatment (visits 3, 4, 5, and 6), the physician will ask for the patient's preference for Tresiba[®] or their previous treatment and enter it in the eCRF.

8.4 Data sources

Physicians or an appropriately qualified and trained delegate will enter data from the patient's medical records in the eCRF.

8.4.1 Patient diaries

Upon providing informed consent, each patient will be given a study diary and provided guidance in its use. There will be 2 diaries, the first one will cover 4 weeks of baseline data (between visits 1 and 2) and the second one will cover the 4 weeks prior to each physician visit (visits 3 to 6). At the visit following completion of the diary, the patient will return his/her diary and will be given a new one. Data from the diary will be entered into the eCRF. The diary will be kept in the source files at the investigational site.

The 4-week diaries will include sections for information such as:

- Insulin dose and time of administration
- Details of missed doses and dose-time flexibility
- Number of SMBG test strips used
- Information related to hypoglycaemic episodes. Each time the patient has a symptom of hypoglycaemia or his/her blood sugar level is below or equal to 3.9 mmol/L (70 mg/dL), the patients will be encouraged to complete the diary (exact time, PG value, assistance required or not)
- Resource use due to hypoglycaemia.

8.4.2 Visit procedures

The physician must keep a patient enrolment log and a log of patients evaluated for but not included in the study throughout the enrolment period. These can be combined in one document.

A sequence of patient numbers will be assigned to each study site. All patients entering the baseline period will receive a patient number that will be used to identify the patient throughout the study. Patients withdrawn from the study retain their patient number, if already given. New patients must always be allocated a new patient number.

Patients who are enrolled in the study will be provided with contact address(es) and telephone number(s) of the physician site and/or staff.

Patients will be asked about any AEs during each visit by the physician or study site staff. This may be done by posing a simple question such as “have you experienced any problems since the last visit?” However, only SADR, MESI, pregnancies and severe hypoglycaemic events (regardless of seriousness or causality) will be collected in this study as specified in Section [10](#).

In case a patient is being prematurely withdrawn from the study the physician will ensure that the procedures for the last visit are recorded, if possible. The primary reason (adverse reaction or other) for discontinuation must be specified in the eCRF.

The study consists of a 4-week baseline period followed by a 12-month (± 45 days) observation period. All visit dates are based on the date the patient started Tresiba[®] medication (Month 0, visit 2). The time window for visits 3, 4, 5, and 6 (Months 3, 6, 9 and 12) is ± 45 days. Visits are not protocol defined but based on the estimated regularity of visits to a treating physician under normal clinical practice. It is not expected that all patients will attend all visits.

8.4.3 Visit 1 Physician plans to initiate Tresiba[®] (Week -4)

The patient will receive complete information about the study both orally and in writing. Informed consent must be given prior to any trial-related data being collected.

The visit will include:

- Signature of informed consent and recording of the date informed consent was given
- Determination of eligibility by checking the inclusion/exclusion criteria (Section [8.2.2](#) and Section [8.2.3](#)). The decision as to which T1DM and T2DM patients will start Tresiba[®] treatment is determined by the treating physician
- Distribution of all PROs to be completed by the patient. This will be done prior to any following steps. The questionnaires will be administered while the subject is in the waiting room or another dedicated room
- Demography – collecting age, sex, ethnicity
- Blood pressure (systolic and diastolic) and height measurements, if available
- Body weight (kg), if available
- Medical history
- Physician will document if the patient is hypo-prone
- Concomitant medications (related to diabetes - including insulin dosing regimen)
- Physician will document if the patient is a high dose insulin user (>80 U/day)
- Collection of the most recent HbA1c and FPG and date of the measurements
- Patients will be interviewed and asked to recall any severe hypoglycaemic episodes in the 6 months prior to this visit
- Distribution of diary and guidance on use.

The patient will be instructed to:

- Continue on current therapy, as prescribed by the physician and lifestyle interventions
- Record in the diary every episode of hypoglycaemia occurring over the following 4 weeks
- Record in the diary insulin dose, time, and date (over the following 4 weeks)
- Record in the diary if any doses are missed and what the patient did
- Record in the diary how many SMBG strips they use over the following 4 weeks
- Record in the diary any resource use due to hypoglycaemia over the following 4 weeks
- Bring the diary to the next clinical visit.

An appointment will be made for their next usual clinical visit (visit 2, initiation) in approximately 4 weeks (+14 days).

8.4.4 Visit 2, Initiation/Baseline (Month 0)

The decision to treat patients is entirely based on the physician's decision in accordance with local practice.

This visit will include:

- Check of inclusion, exclusion and withdrawal criteria (see Sections [8.2.2](#), [8.2.3](#) and [8.2.4](#))
- Distribution of all PRO questionnaires to be completed by the patient. This will be done prior to any following steps
- Body weight (kg), if available
- Concomitant medications, including current insulin dosing regimen, will be recorded
- Collection of the most recent HbA1c and FPG and date of the measurements
- Collection of safety information. Patients will be asked about any AEs as part of standard care. Each SADR, severe hypoglycaemic episode (regardless of physician's evaluation of seriousness and causality), MESI, and pregnancies will be recorded on a separate AE form and SIF according to existing reporting procedures and timelines
- Collection of diary and distribution of a new one
- The patient will be asked what their total daily dose of bolus insulin was on the day prior to the visit, if applicable
- The patient will be asked if their insulin treatment required them to change any social, leisure, and working time activities
- Physician will document the reason for switching or not switching to Tresiba[®] treatment as applicable
- Based on physician decision, patients will commence treatment on Tresiba[®]

The patient will be instructed to:

- Continue on current therapy including Tresiba[®], as prescribed by the physician and lifestyle interventions
- Record in the diary every episode of hypoglycaemia occurring over the 4 weeks prior to the next visit
- Record in the diary insulin dose, time, and date (for 4 weeks prior to the next visit)
- Record in the diary if any doses are missed and what the patient did, and details of dose-time flexibility
- Record in the diary how many SMBG strips they used over the 4 weeks prior to the next visit
- Record in the diary any resource use due to hypoglycaemia over the 4 weeks prior to the next visit
- Bring the diary to the next clinical visit.

